10.3 HEALTH-ECONOMIC ANALYSES

We will assess the full economic costs of each randomised group from time of admission to hospital until death or 28 days' follow-up. While the trial defines re-admission to hospital as an endpoint, for an economic evaluation, hospital re-admission will be included as a cost. A full economic costing approach includes financial as well as opportunity costs and is necessitated by the reality of severely constrained capacity within LMIC health systems. Our approach to costing establishes the utilisation of health services (e.g. inpatient days, diagnostic tests, medication and oxygen) directly from trial data specific to each randomised group. Within a decision analytic modelling framework, these utilisation estimates are multiplied by the full economic or site-specific unit cost of each service, diagnostic test or medicine. Unit costs are computed using a combined bottom up and step down approach, as appropriate [57]. When valuing resources within the cost analysis that are paid from

the research budget, we will use routine public sector salaries for staff and will seek to cost antibiotics that are sourced specifically for the trial at a level commensurate with a potential public sector funding decision in LMIC. In addition, care will be taken to exclude any costs that are incurred only as part of the research.

The data collection at the health system level will be complemented by a comprehensive assessment of costs incurred by households. These costs do not only include out-of-pocket expenditures for medical services (which we expect to be small because the trial will cover related costs), but also costs for transport to facilities, local food and accommodation, and income losses due to absences from work.

Once we have estimated our unit costs and utilisation, we will build a decision analytic model in order to estimate the cost per child treated within each randomised group, from time of first admission until 28 days follow-up. Deterministic sensitivity analyses will assess the impact of key parameter uncertainty (e.g. the cost of antibiotics within a scale-up scenario) and probabilistic sensitivity analysis will assess uncertainty around the relevant utilisation and outcome estimates from the trial [57]. Then, using outcome data from the trial and secondary sources as necessary, we will estimate a range of incremental cost-effectiveness ratios, including the cost per additional child cured, cost per life-year gained, and cost per DALY averted. DALYs are the addition of Years of Life Lost (YLL) and Years Lived with Disability (YLD) [57, 58]. DALYs will be calculated in two steps. First, for children dying during the trial, the life-year estimate (as described above) is equivalent to YLL. Secondly, for all children, a disability weight will be applied to an estimate of the days spent with CAP. This disability weight for childhood CAP will be sourced from the WHO [59]. Put together, this will enable an estimation of DALYs, and DALYs averted within each trial group.

One of the key intentions of economic evaluation is to promote health care decisions that maximize population health within the available budget. To achieve this, a generic measure of outcome is needed in order to compare (in theory) across the full spectrum of diseases and patient groups within the particular setting [60]. Following this logic, the key ratio to be used will be the incremental cost per DALY averted (the incremental cost-effectiveness ratio (ICER)). Determining cost-effectiveness then requires the comparison of this ICER to other claims on limited resources (represented by a cost-effectiveness threshold (CET)). If the $ICER < CET$ the intervention may be deemed “cost-effective”. The choice of CET will be based upon knowledge of the ICERs in recent funding decisions within the country health systems as well as international estimates.

One of our main economic hypotheses is that the earlier discharge of children will substantially lower the financial and time burden to families, and that these differences will be particularly important for the poorest strata in each country. To quantify these differences, we will collect data on household’s human capital and living conditions and then classify households into site-specific quintiles. We will then estimate interacted impact models in a first step to assess whether health impacts vary across socio-economic subgroups. In a second step, we will quantify the total financial burden for all households, and quantify the share of households experiencing catastrophic expenditures. Catastrophic expenditure will be defined as total cost exceeding specific fractions of total monthly household income, with thresholds ranging between 10 and 50% [61]. Household incomes will be computed based on the observed asset holdings using national surveys as reference points [62]. The generated evidence will complement the standard cost-effectiveness analysis (which abstracts from equity aspects) by assessing the overall equity and impact of these treatment regimens in general, and by assessing the extent to which these regimens can reduce socioeconomic gaps in particular.

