9.2.4 PROTECTION FROM BIAS

It is not practical to use placebos for the multi-drug multi-duration regimens used in this trial, given the relatively large differences in numbers of tablets across the different weight-bands. Further the co-amoxiclav and amoxicillin tablets are different meaning a “double dummy” approach would be needed (each child receives either active co-amoxiclav and placebo amoxicillin or placebo co-amoxiclav and active amoxicillin). Introduction of placebo would therefore increase the pill burden substantially and will be logistically infeasible. It is also not ethical to give children sham IV treatment, which would also defeat one of the key purposes of the trial which is to investigate oral step-down as a mechanism to reduce length of hospitalisation.

Therefore, to counter the possibility of bias, objective outcome measures have been chosen as much as possible. The primary endpoint is re-admission to hospital or death within 28 days post-randomisation. Hospital admissions are clinically significant events and it is reasonable to assume, therefore, that they will be approximately ascertained without bias. The trial will pay for visits to the hospital, if required, within the follow-up period (where healthcare is not free of charge), meaning that parents/carers will have a reason to come back to the original hospital rather than go elsewhere. Every effort will be made to minimize losses to follow-up and to ascertain outcomes completely, thus avoiding bias from differential ascertainment between the randomised groups. Any child lost-to-follow-up will be traced for vital status based on location and mobile phone data verified before discharge (with consent for this). To further protect from bias, an independent Endpoint Review Committee will adjudicate on the causes of death and of hospitalisation (to enable an unbiased assessment of the secondary outcome, CAP-related readmission/death) and whether (without knowledge of actual randomisation) events were unlikely, possibly/probably or uncertainly to have been related to each intervention, were those affected to have received them. This will increase the objectivity of these assessments and increase consistency between sites.

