Following recommendations in adults [52], we have avoided using a “test of cure” approach to define endpoints precisely because of substantial challenges in its unbiased assessment outside a placebo-controlled trial. In paediatric CAP, particularly in very young children, symptom recovery scores are also highly subjective and therefore we have not considered these as primary or secondary endpoints either.

Secondary outcomes include length of stay; hospitalisations will be paid for by the trial (if not free of charge) so there will be no pressure to discharge children differentially between randomised groups. Other secondary outcomes include change in antibiotics: the trial protocol (**Table 8**) and manual of operations will contain criteria supporting failure of antibiotic therapy and need to switch, promoting consistency in antibiotic management regardless of original randomisation and minimizing bias. The trial is, however, designed to be pragmatic and reflect what would happen in the real-world where, for example, WHO guidelines were to recommend stepping down to oral therapy for 4 days total duration; in that some children would still need to switch antibiotics and others continue beyond 4 days. What the trial will provide is estimates of these proportions and overall effects on outcomes.

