11.2 ETHICAL CONDUCT

11.2.1 ETHICAL CONSIDERATIONS

The risks of the safety of children enrolled in the trial relate to the inherent risks of the drugs being studied. All drugs have side-effects, including antibiotics. The main possible side-effects of both the drugs being tested in the trial (amoxicillin and co-amoxiclav) are diarrhoea, and nausea/vomiting. Very rarely children can have an allergic reaction to amoxicillin. However, those randomised to oral step-down will have a shorter period with IV lines, which may reduce complications. Parents/carers of children randomised to 5 days' IV will receive travel costs for any additional days their child remains in hospital solely for the purpose of receiving intravenous antibiotics within the trial, since a few of these children might otherwise be discharged early on oral antibiotics depending on local practice (site-specific). The trial will directly evaluate whether these potential risks are outweighed by potential benefits.

An additional CRP test is required for eligibility: this is to avoid including a large number of children in the trial without bacterial infections (who therefore do not need antibiotics) and hence potentially miss important effects in children with bacterial infections. Some of the trial sites already do a

baseline CRP in children admitted with CAP. For the trial we will standardise CRP testing to use a point-of-care device which can be done using a finger or heel prick rather than an additional venous blood draw. Admitted children will have finger/heel pricks for glucose measurement during admission and these are more acceptable to parents/carers.

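### Section 10.3 counts household costs as incurred while the trial pays hospital charges, so in fee-charging settings the step-down versus 5-day IV difference in mean family burden is understated

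*Protocol*

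**What the plan says.** Protocol section 10.3 adds household costs, as families incur them, to the health-system costing. The medical part is "out-of-pocket expenditures for medical services (which we expect to be small because the trial will cover related costs". The non-medical part is listed in the same sentence: "but also costs for transport to facilities, local food and accommodation, and income losses due to absences from work".

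Section 10.3 then names earlier discharge lowering the financial and time burden on families as one of the main economic hypotheses. To examine it, "we will quantify the total financial burden for all households, and quantify the share of households experiencing catastrophic expenditures", with catastrophic expenditure defined as total cost above 10% to 50% of monthly household income.

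Section 9.2.4 states what the trial pays: "hospitalisations will be paid for by the trial (if not free of charge" and, for follow-up, "The trial will pay for visits to the hospital, if required, within the follow-up period (where healthcare is not free of charge". Sections 5.2.1 and 11.2.1 add a payment for one group only: "Parents/carers of children randomised to 5 days' IV will receive travel costs for any additional days their child remains in hospital". Travel to the week 4 visit is paid for everyone (section 6.10).

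Section 10.3 has rules for resources that the research budget pays for, but they sit on the health-system side: "we will use routine public sector salaries for staff", trial antibiotics are re-priced, and "care will be taken to exclude any costs that are incurred only as part of the research".

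**The concern.** The economic question is about routine care. Section 6.8.1 wants costs that represent African countries in general, and the lay summary gives families' usual liability for the hospital stay as the reason for studying its length. The trial removes that liability for its participants, and section 10.3 then measures what is left.

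The removal is not neutral between groups. A waived daily charge is worth more to a family whose child stays longer, and the 5-day IV group stays longest by design. The comparison meant to show the financial benefit of early discharge is therefore made after part of that benefit has been paid away. At stake is whether the household and equity results describe routine practice or trial conditions.

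**Working it through.** The protocol gives no household cost, fee level or catastrophic-expenditure rate, so there is no planned figure to reproduce. The check has three steps: where the subsidy falls, what it does to a difference in means, and what it does to a difference in shares above a threshold.

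**1. Where the subsidy falls.** Inputs: 5 inpatient days in the IV group (section 5.2.1) and 1 to 3 IV days expected in the step-down groups (section 1.4.2).

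Extra trial-paid days = 5 − IV days in step-down = 5 − 3 to 5 − 1 = **2 to 4 days per child**, if discharge promptly follows the switch. Some step-down children will stay on as inpatients, for example on oxygen (section 5.3.1), which shortens the gap.

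Readmissions do not offset this. Taking the 9% to 15% primary-outcome rates in section 9.3.1 as an upper limit for readmission, and assuming a 4-day stay: 0.09 × 4 = 0.36 to 0.15 × 4 = 0.60 trial-paid days per child. Even the whole of this is below the 2-day lower figure.

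**2. Difference in mean household cost.** Let F be the share of the normal household cost per inpatient day that consists of user fees. If the trial pays the fees, then

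measured difference ÷ true difference = 1 − F.

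| F (assumed) | Measured as % of true |
|---|---|
| 0 (care is free) | 100% |
| 0.25 | 75% |
| 0.50 | 50% |
| 0.60 | 40% |

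Adding the fees back restores 100% in each row.

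**3. Share of households with catastrophic expenditure.** This is an illustration by simulation, and all inputs are assumptions: lognormal monthly income (median 1, log-SD 0.8), true household cost of 6% of median monthly income per inpatient day, and stays of 5 days against 2. A household counts if days × 0.06 × (1 − F) ÷ income exceeds the threshold.

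| Threshold | Quantity | F = 0 (true) | F = 0.25 | F = 0.50 |
|---|---|---|---|---|
| 10% | 5-day share | 0.916 | 0.846 | 0.696 |
| 10% | difference, 5 vs 2 days | 0.326 | 0.398 | 0.434 |
| 25% | 5-day share | 0.591 | 0.448 | 0.262 |
| 25% | difference, 5 vs 2 days | 0.411 | 0.348 | 0.225 |
| 50% | 5-day share | 0.262 | 0.159 | 0.066 |
| 50% | difference, 5 vs 2 days | 0.225 | 0.143 | 0.062 |

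The share falls in each group as F rises, but the difference between groups does not always shrink. At the 10% threshold most 5-day households exceed the limit even without fees, so removing fees lowers the 2-day share more (0.916 − 0.326 = 0.590 down to 0.696 − 0.434 = 0.262) than the 5-day share (0.916 to 0.696).

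**The case against.** Four objections carry weight.

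**Only one component is affected.** Food, accommodation, lost income and time are counted, no general subsidy of them is stated, and they too grow with inpatient days. The hypothesis covers time as well as money. This stands: a reader might infer that the household analysis as a whole is biased towards no difference, and the documents do not support that.

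**The trial pays only where care is not free**, and the protocol does not say at which sites that applies. This stands, and it makes the effect conditional.

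**Travel is not shown to be recorded net.** The payment specific to the IV group invites the inference that transport cost is also suppressed there. But section 6.8.1 takes transport cost from caregiver report and checks it against local distance and fare, which points to gross cost. Sections 5.2.1 and 11.2.1 also expect that only a few of these children would otherwise go home early. Adding reimbursements to costs that are already gross would count them twice, mostly in the IV group.

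**The valuation rule may belong in a separate analysis plan.** This stands only in part. The protocol is not merely silent: it sets an as-incurred measure, accepts that the trial will make medical spending small, and uses the result to judge family burden. Its rules for research-paid resources remove or re-price provider costs, and none restores a waived fee to the household.

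A reader might also multiply the two figures in section 1.1, up to US$600 per episode and a saving of around 40% from early switch, to size the missing difference. That is not sound. The saving comes from high-income settings, and the US$600 is the cost of inpatient care, with nothing to show that families bear it.

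**Conclusion.** The point holds for medical fees, in settings where families are normally charged. There, the step-down versus 5-day IV difference in mean financial burden is understated by the fee share of the daily household cost. Catastrophic-expenditure shares are too low in each group, and the difference in those shares is distorted: smaller at some thresholds within the protocol's 10% to 50% range, possibly larger at others. Where care is free, there is no effect.

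The size cannot be fixed from the protocol, because neither the fee share nor the fee-charging sites are given; the percentages above are illustrations. The excess of 2 to 4 trial-paid days rests on prompt discharge after 1 to 3 IV days. The point concerns an ancillary analysis. It does not touch the primary outcome or the sample size, and the provider-side costing has its own valuation rules.

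**What to change.** In section 10.3, state that:

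- household burden and catastrophic expenditure will be computed with trial-paid user fees added back, as site charge × inpatient days and items used, including trial-paid readmissions and follow-up visits;
- as-incurred household costs will be reported alongside, so that readers see both the routine-care and the trial-conditions figure;
- transport will be valued gross of any trial reimbursement, and reimbursements will not be added to reported costs that are already gross.

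The cost is a few sentences and a small extra analysis step. Section 6.8.1 already plans to collect charges for the resources used and resource use for each child. The downside is reliance on site charge data, including confirmation of which sites charge families and whether a daily ward fee applies.

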11 REGULATORY & ETHICAL ISSUES

11.1 COMPLIANCE

11.1.1 REGULATORY COMPLIANCE

The trial complies with the principles of the Declaration of Helsinki version 7 of 2013 [63].

It will also be conducted in compliance with the approved protocol, the principles of Good Clinical Practice (GCP), the EU General Data Protection Regulation 2016/679 and the UK Data Protection Act (DPA number: Z6364106).

11.1.2 SITE COMPLIANCE

The sites will comply with the principles of GCP as laid down by the ICH topic E6 (Note for Guidance on GCP) and applicable national regulations. An agreement will be in place between the sites and the CTU, setting out respective roles and responsibilities (see [Section 13](#)).

The sites will inform the CTU as soon as they are aware of a possible serious breach of compliance, so that the CTU can report this breach as necessary. For the purposes of this protocol, a 'serious breach' is one that is likely to affect to a significant degree:

- The safety or physical or mental integrity of the children in the trial, or
- The scientific value of the trial

11.1.3 DATA COLLECTION & RETENTION

CRFs\worksheets, clinical notes and administrative documentation should be kept in a secure location (for example, locked filing cabinets in a room with restricted access) and held for a minimum of 25 years after the end of the trial. During this period, all data should be accessible, with suitable notice, to the competent or equivalent authorities, the Sponsor, and other relevant parties in accordance with the applicable regulations. The data may be subject to an audit by the competent authorities. Medical files of children in the trial should be retained in accordance with the maximum period of time permitted by the hospital, institution or private practice.

11.2 ETHICAL CONDUCT

11.2.1 ETHICAL CONSIDERATIONS

The risks of the safety of children enrolled in the trial relate to the inherent risks of the drugs being studied. All drugs have side-effects, including antibiotics. The main possible side-effects of both the drugs being tested in the trial (amoxicillin and co-amoxiclav) are diarrhoea, and nausea/vomiting. Very rarely children can have an allergic reaction to amoxicillin. However, those randomised to oral step-down will have a shorter period with IV lines, which may reduce complications. Parents/carers of children randomised to 5 days' IV will receive travel costs for any additional days their child remains in hospital solely for the purpose of receiving intravenous antibiotics within the trial, since a few of these children might otherwise be discharged early on oral antibiotics depending on local practice (site-specific). The trial will directly evaluate whether these potential risks are outweighed by potential benefits.

An additional CRP test is required for eligibility: this is to avoid including a large number of children in the trial without bacterial infections (who therefore do not need antibiotics) and hence potentially miss important effects in children with bacterial infections. Some of the trial sites already do a

baseline CRP in children admitted with CAP. For the trial we will standardise CRP testing to use a point-of-care device which can be done using a finger or heel prick rather than an additional venous blood draw. Admitted children will have finger/heel pricks for glucose measurement during admission and these are more acceptable to parents/carers.

Some children will also have blood taken for clinical management and also for research blood tests (PK in particular). The volumes of blood required will be minimized wherever possible and are within the maximum locally agreed volumes. For intensive PK, a venous cannula will be used so that children do not undergo repeated venepuncture. We will also use anaesthetic cream to reduce the impact of cannulisation in children having blood draws for the pharmacokinetic substudy. Travel costs will be provided to parents/carers for the PK day (when their child may need to spend additional time in hospital). Nasopharyngeal and peri-rectal swabs will be collected if consent is given in a subset of children. Samples will be taken from a nappy if the child is wearing one or directly of faecal material if a stool is passed, avoiding additional samples being taken. The risks of rectal swabbing are small and will be minimised by training and adherence to a standardised MOP.

For staff involved in the trial, the only risk occurs from venepuncture.

Children will be informed fully of known risks and possible benefits by means of a patient information sheet for parents/carers, and this will be reinforced by discussions with the trial research teams at the individual sites prior to enrolment.

Children's confidentiality will be maintained throughout the trial. Data submitted on CRFs\worksheets to trial sites and CTU, and samples sent to central testing facilities, will be identified only by the Study ID (including random check letters to improve accuracy of identification, as well as date, and time for PK samples).

Week 4 follow-up will be face-to-face wherever possible for all children, and other follow-up contacts will be via telephone where possible. Travel costs for the additional 4-week visit will be provided to compensate participating families for their time, in line with local ethics policies.

Cost and utilisation data will be collected at the site level and through CRFs\worksheets. This data will remain anonymous (in terms of staff and patient names and identifiers) and will only be used for the purpose of estimating the cost and cost-effectiveness of different treatment strategies as well as their equity impacts at household level.

